6.5. Overall Survival

Overall survival is defined as the time from the date of the first dose start date to the date of death due to any cause. Patients without documentation of death at the time of the data cutoff for analysis will be censored at the date the patient was last known to be alive or the data cutoff date, whichever is earlier. The last known alive date is the last record in the study database. This date may be the maximum of the last visit date or last contact date, including telephone follow-up where the patient is known to be alive.

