6.6. Final Study Evaluation or Unscheduled/Early Termination Visit

To be conducted 14 days after the last dose of study drug or in the event of premature study termination

- 12-lead electrocardiogram (EKG)
- Physical examination (complete)
- Pregnancy test, if applicable
- Vital signs
- Blood samples
 - CBC (with differential and platelet count)
 - Serum chemistry panel
 - PT/PTT
 - Serum sample for HAHA (frozen, to be shipped to Sponsor for analysis)
- Urinalysis
- Concomitant medications (continued, changed)
- Adverse event reporting

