6.7. Long-Term Follow-Up

After completing the final study evaluation, follow-up continues for patients who have not progressed with assessments including CT or MRI studies performed every 3 months for up to 2 years or until progression of disease or initiation of other treatment. Follow-up will also include physical exam, CBC, chemistries, CCI [REDACTED]

(Note: MRI abdomen and pelvis with contrast may be done in situations where a CT with contrast is equivocal or contraindicated. A non-contrast chest CT should be done for patients requiring an MRI of the abdomen and pelvis).

Follow-up is also required at least every 3 months until resolution or stabilization for any treatment-related abnormalities that warrant continued monitoring in patients who progressed and otherwise would have completed the study.

Adverse events and concomitant medications reported at any follow-up visits will include outcome of any ongoing unresolved events, new events attributed to the study treatment, deaths, hospitalizations, and infectious episodes requiring prescription or IV anti-infectives or GI toxicity.

All patients will be followed every month for survival, which may be by telephone. Patients will not be followed beyond 2 years from final study evaluation.

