9.3. Recording Information on AEs

All AEs, whether observed by the Investigator, elicited from, or volunteered by the patient, will be recorded including: duration, severity, relationship to the study medication, treatment, action taken with respect to the study medication and outcome. When possible, all events should be reported in diagnostic terms or the most acceptable medical terms in order to interpret safety information accurately.

The investigator must review all laboratory and test data and record any adverse events. The same format will be used as for other adverse events, regardless whether related to study therapy or not, including event severity grading, attribution, and resolution. A summary listing of all adverse events occurring during the past year on this study will be provided in progress reports reported to regulatory authorities.

The investigator will notify Immunomedics or its designee if he/she becomes aware at any time, during or following the study, of the occurrence of death or new malignancy involving the participant of a clinical trial, even though the event may not appear to be drug related.

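### SAP 6.5 sets no end-of-follow-up limit on OS deaths, so if deaths are recorded after survival contact stops, OS beyond about 24 months can be biased downward

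*SAP*

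**What the plan says.** SAP 6.5 measures OS from first dose "to the date of death due to any cause". The rule for the rest begins "Patients without documentation of death at the time of the data cutoff for analysis will be censored at the date"; the full provision is that such patients are "censored at the date the patient was last known to be alive or the data cutoff date, whichever is earlier". On the alive date it adds: "The last known alive date is the last record in the study database". It places no limit on deaths other than the cut-off.

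Protocol 6.7 provides monthly survival contact but caps it: "Patients will not be followed beyond 2 years from final study evaluation". Protocol 6.6 fixes the starting point of that cap, the final study evaluation: "To be conducted 14 days after the last dose of study drug or in the event of premature study termination".

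Protocol 9.3 has no such cap. The investigator must notify the sponsor on learning of a death, in these terms: "if he/she becomes aware at any time, during or following the study, of the occurrence of death". Apart from new malignancies, it asks for nothing comparable about patients who are still alive.

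SAP 3.1 describes the monthly survival follow-up without mentioning the 2-year limit. SAP 6 names Kaplan-Meier as the OS method and rules out formal hypothesis testing.

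**The concern.** Kaplan-Meier needs the length of follow-up to be unrelated to the outcome. Past the 2-year limit, the three rules together break that condition. A patient who dies and is reported stays in the risk set until death. A patient who lives is normally censored at the last contact, near the limit. The late risk set is therefore too small for the deaths counted in it, the late hazard is overstated, and the tail of the curve is too low.

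The SAP does restrict deaths for its other time-to-event endpoints. In 6.4, a death counts for PFS only while the patient is on study and either treated or being assessed for response. In Table 4, a death after two or more missed assessments is censored for duration of response. OS has no equivalent rule.

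What is at stake is the plotted tail, any late survival rate quoted from it, and any median or upper confidence limit beyond about 24 months. OS is a secondary endpoint in nine single-arm populations, so no control arm exists in which the same artefact would cancel.

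**Working it through.** The documents give no OS rate, event count or power for OS, so there is no plan figure to reproduce. The check has three parts.

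**1. Who can be affected (dates from the documents; 1 month = 30.4375 days).**
- Earliest possible limit after first dose: 14 days + 2 years = 0.46 + 24, about 24.5 months. It comes later for patients treated longer, and could come slightly earlier after premature termination.
- Planned final cut-off: 1 March 2019 (SAP 4 and 9). The limit falls before cut-off only if the final evaluation was before 1 March 2017, which means a first dose no later than about 15 February 2017.
- mTNBC enrolment stopped on 14 February 2017 (SAP 3.3): 745 days, or 24.5 months, before cut-off. mTNBC patients can therefore reach the limit.
- The last patient in the study was enrolled on 22 June 2017: 617 days, or 20.3 months, before cut-off. That patient cannot reach it.
- All patients are under survival contact up to about 24 months, so estimates to that point do not change.

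**2. Direction.** At a time t beyond 24 months, let λ be the true hazard. Let A be the number alive and not yet past the limit, and C the number alive, past the limit and not yet at cut-off. Let q be the chance that a patient in C dies before cut-off, and r the share of those deaths that reach the database. If survivors have no record after the limit:

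- deaths counted per unit time = λ(A + rC)
- risk set in the database = A + rqC
- estimated hazard = λ(A + rC)/(A + rqC)

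This equals λ if r = 0 or C = 0. It exceeds λ when r > 0, C > 0 and q < 1. The error can only run downward in survival, and it needs both late reporting and patients past the limit.

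**3. Size.** Kaplan-Meier was simulated with 400,000 patients per scenario and exponential OS. None of these inputs is in the documents: OS median, time on treatment, accrual pattern, r.
- Set 1: uniform entry over 49 months to February 2017, mean time to last dose 6 months.
- Set 2: uniform entry from 30 May 2012 (protocol release, used only as a bound) to 22 June 2017, median treatment 3 or 6 months.

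| Assumptions | OS at | True | r = 25% | r = 100% | Understated by (points) |
|---|---|---|---|---|---|
| Set 1, median OS 12 | 36 mo | 12.5% | 11.3% | – | 1.2 (r = 25%) |
| Set 1, median OS 18 | 36 mo | 25.0% | 23.2% | 20.9% | 1.8 to 4.1 |
| Set 2, treatment 3, median OS 8 | 36 mo | 4.4% | 4.0% | 3.7% | 0.4 to 0.7 |
| Set 2, treatment 3, median OS 13 | 36 mo | 14.7% | 13.2% | 12.1% | 1.5 to 2.6 |
| Set 2, treatment 6, median OS 13 | 36 mo | 14.7% | 13.9% | 12.9% | 0.8 to 1.8 |
| Set 2, treatment 3, median OS 18 | 36 mo | 25.0% | 22.3% | 20.5% | 2.7 to 4.5 |
| Set 2, treatment 3, median OS 13 | 48 mo | 7.7% | 4.7% | 4.1% | 3.0 to 3.6 |
| Set 2, treatment 3, median OS 18 | 48 mo | 15.7% | 9.3% | 7.9% | 6.4 to 7.8 |

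For median OS of 12 to 18 months, the 36-month range is 0.8 to 4.5 points, or about 1 to 5. With r = 0 in Set 2 (median OS 13), 36-month OS is 14.7%, the true value. When every patient is first dosed in the last 24.5 months before cut-off, nobody passes the limit and the bias is zero for any r. Censoring everyone at the earlier of the limit and cut-off gives 36-month OS of 14.6% against 14.7% (median 13) and 25.0% against 25.0% (median 18) in Set 2.

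**The case against.** Several points on the other side have force.

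- **Protocol version.** SAP 1 is written to the protocol of 24 April 2017, with Amendments 1 to 11. The 2-year limit is quoted from the revision of 23 January 2020, which is later than the planned cut-off, and SAP 3.1 does not mention the limit. The documents do not show whether it was in force earlier. This stands and must be confirmed.
- **Whether late deaths are counted is inferred.** Protocol 9.3 is a notification duty within the adverse event section. It does not say that such a notice reaches the locked database, and nothing shows that any late death was recorded. This stands. SAP 6.5 as written would still count one that did.
- **Survivors can have later records.** Protocol 9.6 continues follow-up of possibly related events after participation ends, and 9.3 also covers new malignancies. This softens the bias. It does not remove it, because such records are incidental.
- **Hidden text.** SAP 6.9 and 11 are partly blacked out, and SAP 10 refers to a separate data-handling document. A rule may exist there, so the point rests on the visible text.
- **Small effect on planned output.** OS is descriptive, and the visible SAP names no late survival rate. For the 108 target mTNBC patients the binomial standard error, a lower bound under censoring, is √(0.125 × 0.875/108) = 3.2 points at 12.5% survival and √(0.25 × 0.75/108) = 4.2 points at 25%. A bias of 1.2 points is about 0.4 of the first, and 4.5 points is about 1.1 of the second. This limits the weight of the point, but the bias would remain however many patients were studied.

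A reader might go further and infer that every OS curve in the study is biased by construction. The documents do not support that. It would need late deaths to have been recorded and every cohort to contain patients past the limit, and neither is shown.

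**Conclusion.** The point holds as a conditional one. Read with the current Protocol 6.7 and 9.3, SAP 6.5 lets follow-up past the 2-year limit depend on whether the patient dies. If late deaths are recorded, OS beyond about 24 months can be biased downward in cohorts with patients whose final evaluation was more than 2 years before cut-off. Under assumed exponential OS with a median of 12 to 18 months and 25% to 100% of late deaths reported, 36-month OS is too low by about 1 to 5 percentage points. The 48-month figures in the table move more, by 3.0 to 7.8 points. These sizes rest on assumed survival, treatment time, accrual and reporting, and on survivors having no record after the limit. The finding does not touch the primary endpoint, OS rates to 24 months or medians below about 24 months. It justifies a small correction to the SAP and does not cast doubt on OS as a whole.

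**What to change.** In SAP 6.5, define a limit for each patient as the earlier of the data cut-off and 2 years after the final study evaluation. Count deaths up to that limit as events. Censor all others at the earlier of last known alive and the limit. State which date to use when the final evaluation did not take place, and that only the cut-off applies to patients who have not yet reached that evaluation.

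List deaths after the limit and report their number by population, which will show at once whether the issue arose. Keep the analysis of all documented deaths as a sensitivity analysis. Where vital status at cut-off is already known for every patient in a population, alive or dead, use that instead.

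Before adopting this, confirm that the 2-year limit applied under the protocol version in force at cut-off.

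The cost is a short addition to the text, one derived date and one extra OS run. The downside is that a few late deaths do not count in the main OS estimate.

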6.6. Duration of Response

Among responders (patients who have a best response of PR or CR), DOR will be calculated as the date of the first evaluation showing documented PR, or CR to the date of the first PD or Death. $DOR = (\text{Earliest Date of Progression or Death} - \text{Date of First PR/CR} + 1) / 30.4375$. For patients not progressing, censoring rules apply. DOR censoring rules are presented in [Table 4](#).

Table 4: Guidelines for Response Assessment and Censoring for Analysis of Duration of Response

Guidelines for Progression Assessment and Censoring for Analysis of Duration of Response			
Condition	Case	Outcome	Date of Progression or Censoring
Objective PD or Death occurred	At or between scheduled assessments or prior to missing 2 scheduled successive assessments	PD / Death	Date of objective PD or Death
	Progression or Death after missing 2 or more scheduled successive assessments	Censor	Date of last adequate response assessment
No objective PD or Death occurred	Initiated other treatment	Censor	Date of last adequate response assessment prior to starting other treatment
	Lost to follow-up	Censor	Date of last adequate response assessment
	Data cutoff	Censor	Date of last adequate response assessment

Abbreviations: CT = Computed tomography, MRI = Magnetic resonance imaging, PD = Progressive disease.

If the onset of response requires evaluations at different times (ie, chest CT on 1 day, abdomen and pelvic MRI several days later) the last measurement date should be used. For progression based on the sum of target lesion measurements at different times (ie, chest CT on 1 day, abdomen and pelvic MRI several days later) the last measurement date should be used. For progression based on new or nontarget lesions, if these are equivocal at 1 assessment and later considered unequivocal progression, the earliest date when progression was suspected should be used. If progression occurred after 2 or more scheduled successive response assessments were missed or inadequate, the outcome will be censored at the last prior adequate assessment. Adequate response assessment is defined as a response assessment other than "not assessed" or "not evaluable" for the determination of duration of response. If objective evidence of progression has not occurred and the patient is either lost to follow-up, died, a new treatment is initiated, or data cut-off occurs, then the outcome will be censored at the last prior adequate assessment.

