6.4. Progression-Free Survival

Progression-free survival is defined as the interval from the first dose start date to the date of disease progression defined as documented PD or death from any cause, whichever occurs first. Death was considered an end point only while the patient was on study and receiving treatment or undergoing response assessments. Patients otherwise without adequate response assessments or without radiologic evidence of progression were censored. Clinical PD was not considered as a PFS event. $PFS = (\text{Earliest Date of Disease Progression/ Death} - \text{First Dose Start Date} + 1) / 30.4375$.

The approach regarding handling of assessments, dates, and censoring presented in [Table 3](#) is based upon RECIST1.1 guidelines ([Eisenhauer et al., EJC, 2009](#)). **CCI**

[figure not shown]

Table 3: Guidelines for Response Assessment and Censoring for Analysis of Progression-Free Survival

Guidelines for Progression Assessment and Censoring for Analysis of PFS		
Case	Outcome	Date of Event/Censoring¹
No adequate response assessment after start of treatment		
Died prior to second scheduled assessment	PD	Date of death
Did not die prior to second scheduled assessment	Censor	Date of first dose
Continued study until objective PD or death		
At scheduled assessment	PD	Date of objective PD
Between scheduled assessments	PD	Date of objective PD or death
After missing 2 or more scheduled assessments	Censor	Date of last adequate response assessment before missed ones
Continued scheduled response assessments without objective PD or death		
Discontinued for undocumented PD, toxicity, other reasons	Censor	Date of last adequate response assessment
Lost to follow-up	Censor	Date of last adequate response assessment
Initiated other treatment	Censor	Date of last adequate response assessment prior to starting other treatment
No objective PD at final assessment	Censor	Date of last adequate response assessment

Abbreviations: CT = Computed tomography, MRI = Magnetic resonance imaging, PD = Progressive disease, PFS = Progression-free survival.

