8. MAJOR PROTOCOL DEVIATIONS

A by-patient listing with major study protocol violations and deviations will be provided for patients in the Overall Safety Population, and major protocol deviations as identified will be summarized for the Target mTNBC, mUC, mBC, and Overall Safety Population.

Protocol Violations to be Programmed

- Inclusion/Exclusion Criteria
 - <2 weeks between previous treatment, immune therapy, chemotherapy, or investigational therapy for metastatic disease and start of treatment with IMMU-132.
- Prohibited Medication
 - Anticancer therapy during treatment with IMMU-132 (fulvestrant; Gemzar; letrozole; nivolumab; paclitaxel; temozolomide).
 - Radiation during treatment with IMMU-132 was not allowed except for pain palliation or prophylaxis.
 - Prophylactic medication of hematopoietic growth factors or blood transfusions before Cycle 1.

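### SAP Tables 3 and 4 censor for other anticancer treatment only when no PD or death is recorded, so, read literally, censoring depends on the later outcome and can distort DOR and, less so, PFS

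*SAP*

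**What the plan says.** **DOR (SAP 6.6, Table 4).** The event row reads "At or between scheduled assessments or prior to missing 2 scheduled successive assessments", and its only exception is PD or death after two or more missed assessments. Censoring for other treatment appears in the other block, headed "No objective PD or Death occurred". The text before the table says "For patients not progressing, censoring rules apply". The note under the table repeats the condition: "If objective evidence of progression has not occurred and the patient is either lost to follow-up, died, a new treatment is initiated". It censors all such patients, and those who reach the cut-off date, at their last adequate assessment. That note censors deaths without PD, whereas the table and the DOR formula count them as events.

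**PFS (SAP 6.4, Table 3).** PD and death are handled under "Continued study until objective PD or death", again with missed assessments as the only exception. The row for other treatment sits under "Continued scheduled response assessments without objective PD or death", with the censoring date "Date of last adequate response assessment prior to starting other treatment". The text limits deaths as PFS events to patients still on study and being treated or assessed.

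**Related text.** SAP 6.8 (swimmer plot) names start of other treatment as a reason for DOR censoring, with no condition on what follows. SAP 8 programs a protocol violation for "Anticancer therapy during treatment with IMMU-132 (fulvestrant; Gemzar; letrozole; nivolumab; paclitaxel; temozolomide"). Protocol 6.7 ends off-treatment scans at progression or other treatment, but follows all patients monthly for survival for up to 2 years.

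**The concern.** Neither table has a row for PD or death that comes after another anticancer treatment. Take two responders who start the same other drug on the same day. If one later has documented PD, that patient falls in the event block, and the time on the other drug counts towards DOR. If the second has no event by cut-off, that patient is censored at the last adequate scan before the drug. Whether follow-up after the switch is used is therefore decided by what happens later.

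The switchers who stay in the risk set after the switch are then exactly those who will have an event, so the estimated hazard after a switch is too high. The curve estimates neither DOR or PFS with follow-up stopped at other therapy nor DOR or PFS regardless of other therapy.

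At stake are secondary, descriptive estimates. They are nevertheless reported for every cancer population, in a single-arm study where such estimates are the result. SAP 4.1 and 6.9 plan sensitivity analyses for the target mTNBC population only.

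**Working it through.** **Step 1: which routes are open.** The plan gives no figure to reproduce, so the first check is whether a PD or death after other treatment can enter the data.

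- *Scheduled PD after IMMU-132 has stopped:* largely closed, because Protocol 6.7 stops scans at other treatment. PD on an unscheduled scan remains possible.
- *PD while still on IMMU-132 plus another anticancer drug:* open. These patients are still in the treatment period with 8-weekly scans (Protocol 6.4), and SAP 8 expects to find such cases.
- *Death, for PFS:* mostly closed by the restriction in SAP 6.4.
- *Death, for DOR:* open under the table, because survival is followed monthly and SAP 6.6 has no such restriction. It closes only if the conflicting note under Table 4 governs.
- *Two missed assessments:* removes late events. It is unclear whether a scan that the protocol no longer schedules can count as missed, so both readings are tried below.

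**Step 2: size on assumed inputs.** The share switching before PD, the hazard after the switch and the true median are not in the documents. Assumptions: exponential times with λ = ln 2 / 8 per month; switching independent of prognosis at rate g = λp/(1−p), so that a share p switches before an event; hazard after the switch λ × HR; 400,000 patients per scenario. Let S be the switch time, T the event time and C the cut-off. The rules compared are:

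- A (always censor): a switcher is censored at S.
- B (tables read literally): a switcher is an event at T if T is recorded before C, otherwise censored at S. *Full* records every later event. *4 months* and *6 months* record only events within that time of the switch, as a rough stand-in for two missed assessments (two 8-week intervals = 112 days / 30.4375 = 3.7 months; two 3-month intervals = 6 months).
- C (ignore the switch).

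Kaplan-Meier medians in months, C uniform on 12 to 36 months:

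| HR | p | A | C | B full | B 4 months | B 6 months |
|---|---|---|---|---|---|---|
| 1.0 | 5% | 7.99 | 7.99 | 7.95 | 7.90 | 7.89 |
| 1.0 | 10% | 8.02 | 8.02 | 7.95 | 7.83 | 7.81 |
| 1.0 | 20% | 8.04 | 8.03 | 7.87 | 7.62 | 7.58 |
| 1.0 | 30% | 8.03 | 8.03 | 7.78 | 7.34 | 7.29 |
| 0.5 | 30% | 8.00 | 8.71 | 8.05 | 7.61 | 7.57 |

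Rule A should return 8.00, so simulation error is up to about 0.04 month. With HR 1, B minus A at 5% is 7.95 − 7.99 = −0.04 to 7.89 − 7.99 = −0.10. At 30% it is 7.78 − 8.03 = −0.25 to 7.29 − 8.03 = −0.74. The 12-month rate at 30% falls from 35.5% (A) to 33.2% (B full) or 30.8% (B 6 months). If no event after a switch is recorded, B equals A.

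**Step 3: follow-up.** Last enrolment was 22 June 2017 and the planned cut-off is 1 March 2019: 617 days / 30.4375 = 20.3 months at least, less the time to response for DOR. With C on 16 to 40 months, HR 1 and p from 10% to 30%, B full gives 7.95 to 7.79 and B 4 months gives 7.78 to 7.33. With C on 6 to 20 months, nearer to an immature cut-off, B full gives 7.85, 7.66 and 7.46 at 10%, 20% and 30%.

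**The case against.** A reader might infer that PFS and DOR in this trial are biased as a matter of fact. The documents do not support that.

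- Scheduled off-treatment imaging stops at other treatment, and PFS deaths are restricted. This stands, and it is why PFS is the less exposed endpoint.
- The list in SAP 8 is of violations to be programmed. It gives no count and does not say that the drugs came before PD. Treatment after first PD is allowed, and patients who took another drug only then already have their event. Nothing in the documents supports a switching share of 10% to 30%.
- The swimmer-plot text treats other treatment as an unconditional reason for censoring, and the block headings could mean no PD up to that treatment. An unconditional rule may well have been meant. But the two sentences in SAP 6.6 point the other way, so a programmer following the tables and text would apply the conditional rule. Text beside Table 3 and in SAP 6.9 is blacked out and may bear on this.
- The direction is not fixed. With the hazard halved, full capture and 16 to 40 months of follow-up, the literal rule lies slightly above always censoring: 8.06 against 8.02 at 10%, and 8.14 against 7.99 at 30%.
- Always censoring at a switch is not neutral either, since patients may switch because they are deteriorating. With a shared gamma frailty (variance 0.5, hazard unchanged, 30% switching, 12 to 36 months), always censoring gave 10.6 months, ignoring the switch 9.55 and the literal rule 9.1. This stands, and it is the reason for the sensitivity analysis below.

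**Conclusion.** The structural defect holds: as written, censoring for other treatment depends on whether PD or death is recorded later, and no row covers an event after other treatment. It can distort DOR, through deaths, unscheduled scans and other anticancer drugs given during IMMU-132. It can distort PFS to a lesser extent, through the last two.

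The size is unknown because the affected share is not stated. For a true median of 8 months and an unchanged hazard, the median shift is about 0.1 month or less at 5% switching and about 0.2 to 0.7 month downward at 30%. It can change sign if the other drug is active, and it is zero if no event after a switch is recorded. These figures rest on exponential times and on switching independent of prognosis.

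ORR does not use these tables, and no hypothesis test is planned. The rule should be corrected because the correction is cheap, not because a material bias has been shown.

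**What to change.** 1. In Tables 3 and 4, add a row above the event rows: a patient who starts non-protocol anticancer therapy before documented PD or death is censored at the last adequate assessment before that therapy, whatever follows. Define which therapies count.
2. Align the Section 6.6 sentence and the note under Table 4 with this row. Resolve the note's censoring of deaths that the table counts as events.
3. For each population, report how many patients started other therapy before PD or death, and how many had a recorded event afterwards.
4. As a sensitivity analysis, count every recorded PD and death regardless of other therapy, and censor no one for it. If this is wanted outside the target mTNBC population, SAP 4.1 and 6.9 need a matching line.

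The cost is one row per table, a small programming change and slightly fewer PFS and DOR events. The primary rule stays open to informative switching, which the sensitivity analysis would help to show. It can use only events that were recorded, so it too is limited by the end of scheduled scans.
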